# **MODIFICATION HISTORY**

Unique Identifier for this Version	Date of the Document Version	Author	Significant Changes from Previous Authorized Version
1.0	21JUL2017	PPD	Not Applicable – First Version

\\SW20RND01\VistaTempDir\Temp28232\Shire\_0624\_209\_SAP\_v1 0.docx PPD Version Number: Document:

Author: 1.0 Version Date: 21Jul2017

Template No: CS\_TP\_BS016 Revision 4 Effective Date: 01Apr2016 Reference: CS\_WI\_BS005

21Jul2017

# LIST OF ABBREVIATIONS AND DEFINITIONS OF TERMS

ΑE adverse event

AE-QoL Angioedema Quality of Life

ATC **Anatomical Therapeutic Classification** 

**ECG** electrocardiogram

C1-INH C1 esterase inhibitor or C1 inhibitor

CI confidence interval

eCRF electronic case report form

HAE hereditary angioedema

HR heart rate

ITT-S intent-to-treat safety

IV intravenous

MedDRA Medical Dictionary for Regulatory Activities

NNA normalized number of angioedema attacks

PCI potentially clinically important

PD pharmacodynamics

PK pharmacokinetics

PT preferred term

Statistical Analysis Plan SAP

SOC system organ class

VAS visual analogue scale

\\SW20RND01\VistaTempDir\Temp28232\Shire\_0624\_209\_SAP\_v1 0.docx Document: Version Number:

Version Date: 21Jul2017

Template No: CS\_TP\_BS016 Revision 4 Effective Date: 01Apr2016 Reference: CS\_WI\_BS005

Author:

Shire
PROTOCOL: 0624-209
Page 7 of 35

# 1. INTRODUCTION

This Statistical Analysis Plan (SAP) provides a technical and detailed elaboration of the statistical analyses of efficacy, safety, pharmacokinetic (PK), pharmacodynamic (PD), and angioedema quality of life (AE-QoL) parameters as described in the final study protocol Amendment 5 dated 30 August 2016. Specifications for tables, figures, and listings are also contained in this document.

# 1.1. BACKGROUND

Hereditary angioedema (HAE) is a rare, autosomal dominant disease caused by an inherited or spontaneous gene mutation on chromosome 11 that results in a quantitative or functional deficiency of C1 inhibitor (C1-INH) protein (Bernstein 2011). Patients with HAE are susceptible to recurrent episodes of debilitating swelling throughout the body. Replacement of C1-INH through intravenous (IV) administration of CINRYZE® (C1 inhibitor [human]) increases serum concentrations of C1-INH antigen (protein volume) and functional C1-INH activity (potency), temporarily restoring the natural regulation of the complement, contact (bradykinin-forming), and fibrinolytic systems. C1 inhibitor replacement therapy can prevent the occurrence of angioedema attacks associated with HAE or stop and control the mechanism that causes swelling if an attack does occur.

CINRYZE® is a highly purified, viral-inactivated, nanofiltered concentrate of C1-INH produced from human plasma.

## 1.2. STUDY RATIONALE

Currently, there is no product approved in Japan for both prevention of angioedema attacks and treatment of angioedema attacks associated with HAE. In clinical trials conducted outside of Japan, CINRYZE® was proven to be safe, well tolerated, and effective for the prevention and treatment of angioedema attacks in a broad age range of patients with HAE (pediatrics through patients ≥65 years old). Overseas studies have shown that self-administration allows patients to manage their disease symptoms with minimal disruption to their daily activities resulting in reduced absences from work or school and overall improvement in quality of life (Cicardi et al. 2013; Caballero et al. 2013). It is expected that CINRYZE® will fulfill an unmet medical need for Japanese patients with HAE, and the present study is being performed to confirm its safety and efficacy in this patient population.

Document: \\SW20RND01\VistaTempDir\Temp28232\Shire\_0624\_209\_SAP\_v1 0.docx

Author: PPD Version Number: 1.0
Version Date: 21Jul2017

Template No: CS TP BS016 Revision 4 Reference: CS WI BS005

Shire
PROTOCOL: 0624-209
Page 8 of 35

1.0

Reference: CS\_WI\_BS005

# 2. STUDY OBJECTIVES

The objectives of the study are to assess:

- The safety and tolerability of CINRYZE® administered by IV infusion in Japanese subjects with HAE;
- The pharmacokinetics (PK) and pharmacodynamics (PD) of CINRYZE® administered by IV infusion in this subject population; and
- The treatment effect of CINRYZE® administered by IV infusion for the prevention of angioedema attacks and treatment of breakthrough attacks in this subject population.

Document: \\SW20RND01\VistaTempDir\Temp28232\Shire\_0624\_209\_SAP\_v1 0.docx
Author: Version Number:

Version Date: 21Jul2017

Template No: CS\_TP\_BS016 Revision 4

Shire
PROTOCOL: 0624-209
Page 9 of 35

1.0

Reference: CS\_WI\_BS005

# 3. STUDY DESIGN

# 3.1. GENERAL DESCRIPTION

This single-period, open-label study will be conducted at multiple investigational sites in Japan. This is an outpatient study; however, subjects may require an overnight stay at the site for those days on which serial PK/PD blood samples are collected. Subjects would be discharged the following day after collection of the 24-hour PK/PD blood sample.

Subjects will be administered CINRYZE® by IV infusion twice weekly (every 3 or 4 days) for 12 weeks. Study drug will be administered to all subjects at the investigational site for Dosing Visits 1 through 8, 16, and 24; during these visits, subjects may also have physical examinations and other procedures performed (see Schedule 1 of the protocol). Other doses of study drug may be administered at the investigational site or at the subject's home.

# 3.2. DETERMINATION OF SAMPLE SIZE

A sufficient number of subjects will be enrolled to ensure that a minimum of 6 subjects complete the study. When 6 subjects have completed the 12-week treatment period, no further subjects will be enrolled; however, all subjects already enrolled in the study will be followed to study completion.

Document: \\SW20RND01\VistaTempDir\Temp28232\Shire\_0624\_209\_SAP\_v1 0.docx
Author: Version Number:

Version Date: 21Jul2017

Template No: CS TP BS016 Revision 4

Effective Date: 01Apr2016

Converight @ 2000, 2010, 2012

#### 4. EFFICACY AND SAFETY VARIABLES

## 4.1. SCHEDULE OF EVALUATIONS

Schedule of evaluations can be found in Schedule 1 of the protocol.

#### 4.2. EFFICACY VARIABLES

#### 4.2.1. Prevention of Angioedema Attacks

The following efficacy endpoints for prevention of angioedema attacks will be assessed:

- The normalized number of angioedema attacks (NNA) recorded during the treatment period, normalized for the number of days the subject participated in the period; and the NNA for historical data normalized for 3 months prior to study drug administration.
- Summary of all attacks during the treatment period and historical 3 month data, including:
  - o Anatomic location.
  - o Severity (intensity).
  - o Average duration of attacks.
  - o Number of angioedema attacks treated with CINRYZE®, non- CINRYZE® C1-INH or not treated with C1-INH (including attacks treated with any medications other than C1-INH or untreated attacks).
- Effects of therapy on quality of life (results of AE-QoL questionnaire).

#### 4.2.2. TREATMENT OF BREAKTHROUGH ANGIOEDEMA ATTACKS

The following efficacy endpoints for treatment of breakthrough angioedema attacks will be assessed by; CINRYZE® treated attacks, non-CINRYZE® C1-INH treated attacks and other attacks (including any medications other than C1-INH and untreated attacks):

- The number of subjects with breakthrough angioedema attacks.
- The number of subjects with 1, 2, 3 or more angioedema attacks.
- The number of subjects who achieve initial improvement and Complete Resolution. Complete Resolution
  is defined as the cessation of all symptoms of the breakthrough angioedema attack since onset of attack.
- Time to initial improvement and time to Complete Resolution.

Document: \SW20RND01\VistaTempDir\Temp28232\Shire 0624 209 SAP v1 0.docx

Author: PPD Version Number: 1.0
Version Date: 21Jul2017

Template No: CS\_TP\_BS016 Revision 4 Reference: CS\_WI\_BS005

Effective Date: 01Apr2016

Elicolive Date: 017 przo 10

PROTOCOL: Page 11 of 35

Additional analysis for breakthrough angioedema attacks treated with CINRYZE® will also be presented for:

- The number of subjects with breakthrough angioedema attacks.
- The number of subjects with 1, 2, 3 or more angioedema attacks.
- Time from onset of attack to time treated by CINRYZE.
- The number of subjects who achieve initial improvement and Complete Resolution. Complete Resolution is defined as the cessation of all symptoms of the breakthrough angioedema attack since onset of attack.
- Time from the start of study drug administration, CINRYZE, for the particular attack to the time of initial improvement and time to Complete Resolution.

#### 4.3. SAFETY ASSESSMENTS

The following will be assessed:

- Adverse events (including treatment-emergent adverse events).
- Summary statistics and changes from baseline to post-baseline for laboratory testing, vital signs, and, if applicable, any electrocardiogram (ECG) findings will be presented.
- Results of C1-INH antibody testing will be reported for individual subjects and summarized as appropriate.

\\SW20RND01\VistaTempDir\Temp28232\Shire\_0624\_209\_SAP\_v1 0.docx Document:

Template No: CS\_TP\_BS016 Revision 4 Reference: CS\_WI\_BS005

Version Number:

Version Date:

1.0

21Jul2017

Effective Date: 01Apr2016

Author:

Shire
PROTOCOL: 0624-209
Page 12 of 35

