6.2 Adverse Event Collection

At each study visit, subjects will be questioned in a general way to ascertain if AEs have occurred since the previous visit (eg, "Have you had any health problems since your last visit?"). Adverse events will be collected from the time informed consent is signed through 7 days after the last dose of investigational product. This includes events occurring during the screening phase of the study, regardless of whether or not the investigational product is administered. In addition, the investigator will report all SAEs that occur through 30 days after the last dose of investigational product to PAREXEL International Pharmacovigilance and the respective Independent Reviewing Authority according to local reporting requirements.

Please refer to Section 9, Adverse and Serious Adverse Events Assessment.

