7.4 Safety Analyses

The following will be assessed:

- Adverse events (including treatment-emergent adverse events).
- Summary statistics and changes from baseline to post-baseline for laboratory testing, vital signs, and, if applicable, any ECG findings will be presented.
- Results of C1 INH antibody testing will be reported for individual subjects and summarized as appropriate.

NOTE: Treatment-emergent events include all adverse events that start during the treatment period (and up to 7 days after the last dose of investigational product) and were not seen at baseline, or were seen at baseline but worsened in frequency and/or severity during the treatment period (and up to 7 days after the last dose of investigational product).

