9.2.4 Serious Adverse Event Collection Time Frame

All SAEs (regardless of relationship to study) are collected from the time the subject signs the informed consent up to 30 days after the last dose of study drug, and must be reported to PAREXEL International Pharmacovigilance within 24 hours of the first awareness of the event.

In addition, any SAE(s) considered "related" to the investigational product and discovered by the Investigator at any interval after the study has completed must be reported to PAREXEL International Pharmacovigilance within 24 hours of the first awareness of the event.

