#### 5.8. ANALYSIS OF SAFETY

#### 5.8.1. ADVERSE EVENTS

Adverse Events (AEs) will be coded using Medical Dictionary for Regulatory Activities (MedDRA) central coding dictionary version 19.0. Events will be classified by system organ class (SOC) and preferred term (PT). Only treatment emergent adverse events (TEAEs) will be summarized.

Treatment-emergent events include all AEs that start during the treatment period and were not seen at baseline, or were seen at baseline but worsened in frequency and/or severity during the treatment period.

The incidence of injection site reaction AEs will also be summarized at PT and SOC level. Injection site reaction AEs are any PT that include the term 'injection site reaction'.

The incidence of TEAEs will be summarized by intensity ('Mild', 'Moderate' or 'Severe') at PT and SOC level. For each subject and PT, only the most severe AE will be counted.

The incidence of AEs related to study drug will be summarized at PT and SOC level. Events with a relationship to study drug classified as 'Possibly Related', 'Probably Related', and 'Definitely Related' will be categorized as 'Related'. If a subject experiences the same event (at PT level) on more than one occasion, then only one event will be counted, and this event will be categorized as 'Related' if any of the events under that PTs are categorized as 'Related'.

The incidence of AE by PT, the incidence of serious AE by PT and SOC, and the incidence of serious AE by PT will also be presented.

Adverse events will be sorted by SOC in alphabetical order, then within SOC, sort PT in descending frequency.

All AEs for each subject, including the same event on several occasions will be listed, giving both preferred term and the original term used by the investigator. Serious AEs will be presented separately on an additional listing.

Document: \\SW20RND01\VistaTempDir\Temp28232\Shire\_0624\_209\_SAP\_v1 0.docx

Author: PPD Version Number: 1.0
Version Date: 21Jul2017

Template No: CS TP BS016 Revision 4 Reference: CS WI BS005

PROTOCOL: 0624-209 Page 21 of 35

1.0

21Jul2017

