## 9. APPENDICES

# 9.1. APPENDIX I – LIST OF STATISTICAL OUTPUTS

#### 9.1.1. LIST OF PLANNED TABLES

Table 14.1.1.1 Subject Disposition (All Screened Subjects)

Table 14.1.2.1 Protocol Deviations (Intent-to-Treat Safety Analysis Set)

Table 14.1.4.1 Demographic and Baseline Characteristics (Intent-to-Treat Safety Analysis Set)

Table 14.1.4.3.1 Summary of HAE History (Intent-to-Treat Safety Analysis Set)

Table 14.1.4.3.2 Summary of Medical History (Intent-to-Treat Safety Analysis Set)

Table 14.1.4.4 Prior Medications and Therapy (Intent-to-Treat Safety Analysis Set)

Table 14.1.4.5 Concomitant Medications and Therapy (Intent-to-Treat Safety Analysis Set)

Table 14.2.1.1 Summary of Angioedema Attacks during Treatment Period (Full Analysis Set)

Table 14.2.1.2.1 Sensitivity Analysis Completed Schedules - Summary of Angioedema Attacks during Treatment Period (Full Analysis Set)

Table 14.2.1.2.2 Sensitivity Analysis Treatment Compliance - Summary of Angioedema Attacks during Treatment Period (Full Analysis Set)

Table 14.2.1.3 Analysis of Clinical Responder Rate – Achieving at least 50%, 70% or 90% Reduction Relative to Historical Data in NNA (Full Analysis Set)

Table 14.2.2.1.1 Summary of Breakthrough Angioedema Attacks Treated By CINRYZE (Full Analysis Set)

Table 14.2.2.1.2 Summary of Breakthrough Angioedema Attacks Treated By Non-CINRYZE C1-INH (Full Analysis Set)

Table 14.2.2.1.3 Summary of Other Breakthrough Angioedema Attacks Not Treated with C1-INH (Full Analysis Set)

Table 14.2.2.1.4 Summary and Change from Baseline on AE-QoL (Full Analysis Set)

Table 14.2.3.1 C1-INH Antigen, Functional C1-INH activity, Complement C4 and C1q (Intent-to-Treat Safety Analysis Set)

Table 14.2.3.2 Antibody Results (Intent-to-Treat Safety Analysis Set)

Table 14.3.1.1 Overall Treatment-emergent Adverse Events (TEAEs) (Intent-to-Treat Safety Analysis Set)

Table 14.3.1.2.1 Treatment-emergent Adverse Events by System Organ Class and Preferred Term (Intent-to-Treat Safety Analysis Set)

Document: \\SW20RND01\\VistaTempDir\Temp28232\\Shire\_0624\_209\_SAP\_v1 0.docx

Version Date: 21Jul2017

Version Number:

1.0

Template No: CS TP BS016 Revision 4 Reference: CS WI BS005

Effective Date: 01Apr2016

Author:

Table 14.3.1.2.2 Serious Treatment-emergent Adverse Events by System Organ Class and Preferred Term (Intent-to-Treat Safety Analysis Set)

Table 14.3.1.3.1 Treatment-emergent Adverse Events by Preferred Term (Intent-to-Treat Safety Analysis Set)

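### Serious-AE tables are limited to treatment-emergent events, but the documents give three different windows, so SAEs on days 8 to 30 after the last dose may be listed without being tabulated

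*SAP*

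**What the plan says.** **Collection.** Protocol 6.2 sets the window for adverse events in general: "Adverse events will be collected from the time informed consent is signed through 7 days after the last dose of investigational product". For SAEs the window is longer. Protocol 9.2.4 says that all SAEs, whatever their relationship to treatment, "are collected from the time the subject signs the informed consent up to 30 days after the last dose of study drug". Schedule 3 carries the adverse event/SAE row through to the 1-Month visit.

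**Definition of treatment emergence.** Three rules are given:
- Protocol 7.4: "Treatment-emergent events include all adverse events that start during the treatment period (and up to 7 days after the last dose of investigational product".
- SAP 5.8.1 repeats that definition without the 7-day extension, so that onset must fall within the treatment period.
- The algorithm in SAP Appendix III (9.3) classes an event as treatment-emergent if it starts on or after the first dose. It has no upper date limit, and it covers fully known dates as well as partial ones.

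**Tabulation.** SAP 4.3 lists "Adverse events (including treatment-emergent adverse events" as a safety variable. SAP 5.8.1 narrows what is summarised: "Only treatment emergent adverse events (TEAEs) will be summarized". Later in the same section, the sentence promising serious-AE incidence has no such limit. The planned outputs do: "Table 14.3.1.2.2 Serious Treatment-emergent Adverse Events by System Organ Class and Preferred Term", and Table 14.3.1.3.2 (by preferred term only) is limited in the same way. Listing 16.2.7.2 covers SAEs without the restriction.

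**The concern.** The protocol extends SAE follow-up more than three weeks beyond the point at which it stops collecting other adverse events. If the serious-AE tables are filtered on a treatment-emergent flag that ends at the last dose, or 7 days after it, events found by that extra follow-up never reach an incidence figure.

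Safety is the first objective listed. Thrombosis has its own study-level stopping rule (protocol 5.5.2), and protocol 1.1.2 reports five serious thrombotic events from the open-label prevention study. A thrombotic SAE found between the 1-Week and 1-Month visits could be missing from both serious-AE tables or present in both, depending on which section of the SAP the programmer follows. The same ambiguity affects non-serious AEs on days 1 to 7 after the last dose, which the protocol counts as treatment-emergent and SAP 5.8.1, read literally, does not.

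**Working it through.** The plan gives no figure to reproduce. The check classifies each onset day after the last dose under the three rules.

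**Inputs**
- SAE collection ends at last dose + 30 days (protocol 9.2.4).
- Collection of other AEs ends at last dose + 7 days (protocol 6.2).
- Rule A: treatment period only (SAP 5.8.1). The section gives no end date, so the last dose is taken as the end.
- Rule B: treatment period + 7 days (protocol 7.4).
- Rule C: onset on or after first dose, with no end (SAP Appendix III).
- 24 doses, twice weekly (protocol Schedule 2). A mean gap of 3.5 days is assumed, the value that SAP 5.8.8 uses.
- Planned minimum of 6 completers (protocol 7.1, SAP 3.2).

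**Step 1. Onset days counted as treatment-emergent, and so tabulated**

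| Rule | Days 1–7 | Days 8–30 | All 30 days |
|---|---|---|---|
| A. SAP 5.8.1, literal | 0 of 7 | 0 of 23 | 0 |
| B. Protocol 7.4 | 7 of 7 | 0 of 23 | 7 |
| C. SAP Appendix III | 7 of 7 | 23 of 23 | 30 |

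Rules A and B differ on days 1 to 7. Rule C differs from both on days 8 to 30. Because non-serious AEs are not collected after day 7, the days 8 to 30 question concerns SAEs only.

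**Step 2. Share of SAE follow-up affected**
- Days 8 to 30: 30 − 7 = 23 days.
- Share of post-dose SAE days: 23 / 30 = 77%.
- Treatment span: 23 gaps × 3.5 + 1 = 81.5 days.
- SAE window from first dose: 81.5 + 30 = 111.5 days.
- Share of that window: 23 / 111.5 = 20.6%, about 21%.

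The second share describes the study's SAE follow-up as a whole. The first describes only the part after the last dose.

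**Step 3. Effect of one event**
One subject with such an SAE among 6 treated is 1/6 = 16.7%. If that subject has the only SAE, the table reads 0% under rules A and B and 16.7% under rule C. The number treated is not given. It cannot be below the number of completers, so with at least 6 completers 16.7% is the upper limit for one affected subject.

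**The case against.** The strongest objection is Appendix III. A reader might infer that SAEs on days 8 to 30 reach no incidence table at all, whichever definition of treatment emergence is used. The documents do not support that. The SAP's own derivation rule has no end date and, if programmed as written, puts all of these events into both serious-AE tables. For the same reason it cannot be said outright that the tables will understate SAEs in the product's favour; that follows only if one of the prose definitions governs.

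Other points on that side also have weight:
- SAP 4.3 restricts nothing. Assessing all AEs is compatible with tabulating some and listing the rest.
- The protocol itself paired a 7-day treatment-emergent window with 30-day SAE collection, and nothing in it requires later SAEs to be tabulated.
- In a study this small, a reader can go through Listing 16.2.7.2 line by line. SAEs are reported within 24 hours, and a thrombotic event stops enrolment pending review.

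These points limit the consequence but do not settle the conflict. Appendix III is headed as a convention for partial dates, while the substantive definition is in 5.8.1. The two give opposite answers, and the SAP does not say which prevails. The natural repair, aligning Appendix III with protocol 7.4, would by itself take the days 8 to 30 SAEs out of the tables. The window and the content of the serious-AE tables therefore need to be settled together.

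**Conclusion.** The point holds as a conditional one. The SAP restricts its AE summaries and both serious-AE tables to treatment-emergent events, and the documents define that term in three ways that change what is counted. Under SAP 5.8.1 or protocol 7.4, SAEs with onset on days 8 to 30 appear only in Listing 16.2.7.2; under Appendix III they are tabulated. SAP 5.8.1 read literally also drops AEs on days 1 to 7 that protocol 7.4 counts, and SAP 6.2 does not declare this as a change from the protocol.

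The days at issue are 23 of 30 after the last dose, or about 21% of SAE follow-up from first dose. The 21% assumes 24 doses at a mean gap of 3.5 days, with the 24th as the last dose. A supplemental dose for a later breakthrough attack, which protocol 6.12.1 allows, would move the window. One affected subject is an incidence of at most 16.7%. Whether any such event occurred is unknown from the documents. Since every SAE is at least listed, this should be corrected, but it does not put the study's safety record out of reach.

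**What to change.** 1. State one end date for treatment emergence, last dose plus 7 days as in protocol 7.4, in SAP 5.8.1, and add the same upper limit to the Appendix III algorithm.
2. Base Tables 14.3.1.2.2 and 14.3.1.3.2 on all SAEs with onset from first dose through 30 days after the last dose, regardless of the treatment-emergent flag. Show treatment-emergent and post-treatment (days 8 to 30) events as sub-rows, and retitle both tables to match.
3. Keep the treatment-emergent rule for non-serious AEs, which are collected only to day 7.

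The serious-AE incidence then covers the full 30-day collection period after the last dose and no longer depends on which definition a programmer follows. The cost is a few lines of SAP text, two table titles and one date filter, with no new data.
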